Diabetes increases the risk of cognitive dysfunction. The incidence of dementia is 1.5 to 2.5 times higher in persons with diabetes than the general population (1). There is evidence that cognitive decline significantly impacts the ability to self-manage diabetes (2). Strategies to prevent cognitive decline in persons with diabetes has not been well

studied. A recent study reported that in persons who had vitamin D deficiency, the risk for all-cause dementia and Alzheimer's was *doubled* (3). Vitamin D receptors are located in the brain, and deficiency of vitamin D has been reported to negatively affect the development of brain and impact both growth factor signaling and neural activity (4, 5). Therefore, providing vitamin D supplementation to improve cognitive function in persons with diabetes who are at greater risk for this comorbid condition is important.

We propose a small, randomized controlled trial to determine the effects of vitamin D₃ supplementation in persons with type 2 diabetes who have symptoms of cognitive impairment. Persons will be randomized to receive either weekly vitamin D₃ supplementation (50,000 IUs) or a matching comparator (5000 IUs) for a period of three months:

Primary Aim: To determine the effect of vitamin D₃ supplementation on cognitive function for persons with type 2 diabetes.

Primary Hypothesis: Persons receiving weekly vitamin D₃ supplementation (50,000 IUs) will have improved cognitive function compared to those receiving the comparator (5000 IUs) at three months.

Secondary Aim: To determine the effect of vitamin D₃ supplementation on diabetes self-management.

Secondary Hypothesis: Persons receiving weekly vitamin D₃ supplementation (50,000 IUs) will have improved self-management compared to those receiving the comparator (5000 IUs) at three months.

The importance of this study is severalfold. Vitamin D supplementation is a low-cost intervention (6), it has minimal side effects (7), and it could have high impact for persons with type 2 diabetes who suffer from cognitive impairment which can significantly affect diabetes self-management.

Background and Significance

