
Table 1: Scheduled Activities

	Screening	Week 0	Week 2	Week 8	Week 13
Depression Screen	X				
Demographics	X	X		X	X
Cognitive Tests	X	X	X	X	X
Questionnaires		X			X
Vitals		X			X
General Nursing Physical		X			

Blood Draw		X			X
Adverse Event Log		X	X	X	X
Dose Management Log			X	X	X
Concomitant Medication Log		X	X	X	X

4. Measurements.

A. Labs will be measured for each time point by Quest Laboratories which is accredited by the College of American Pathologists (CAP) and Clinical Laboratory Improvement Amendments (CLIA). **Serum vitamin D** will be measured by liquid chromatography/tandem mass spectrometry (LC-MS/MS) which is the standard for the measurement of vitamin D and its components. This method provides a total 25 hydroxyvitamin D (25 OH- D) which includes 25 (OH) D₂ and 25 (OH) D₃. Thus, we will be able to determine the effectiveness of vitamin D₃ supplementation. **Calcium** will be measured using a cardiometabolic profile. The **hemoglobin A1c** will be assessed using the DCA analyzer which is the practice in our diabetes center. Also, inflammatory markers will be collected. Potential confounders for vitamin D include sun exposure and diet and will be measured as follows: **(1) Sun Exposure:** Season of study enrollment will also be recorded and the Cancer Sun Exposure Tool which is 14 items and assesses sun exposure and use of sunscreen (35), **(2) Dietary Intake:** The Block Calcium and Vitamin D Screener will be used. This tool was developed from the NHANES 1999-2001 dietary recall data. It includes 19 food items, 3 supplement questions, and questions to adjust for food fortification practices (36).

B. Self-Management measures include: **(1) Diabetes Self-Care Inventory** (15 items) assesses a patient's perceptions of the degree to which they adhere to treatment recommendations for diabetes self-care (1= never do it to 5= always do it). This tool does not presume that all individuals have the same treatment prescription and thus is able to assess adherence to different treatment regimens (e.g., insulin or not taking insulin) (37, 38). **(2) Diabetes-Related Distress** (PAIDS, 20 items) measures the current burden of diabetes and its treatment. The responsiveness of the tool to detect changes in distress has also been established using data from seven prospective diabetes intervention studies (39).

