A meta-analysis based on a sample size of $N = 7,688$ by Etgen et al. (2012) was used to determine a sample size with suitable power for this trial. In their study, individuals with insufficient vitamin D were nearly three times (95% CI: 1.91 – 3.00) more likely to experience executive dysfunction than individuals who were vitamin D sufficient. Our study is powered to test the null hypothesis that performance on a battery of executive functioning tests is equal between individuals receiving high dose vitamin D therapy and those receiving low dose vitamin D therapy. These executive function scores are assumed to be standard scores ($\mu=100$, $SD=15$).

With a proposed total sample size of 62 subjects assigned to the 50,000 IU and 5,000 IU dose treatment arms using a 1:1 allocation, the study has power of 81.1% to yield a statistically significant result. This computation assumes a two-sided alpha level of 0.05, that the mean difference between the two groups is less than one standard deviation (mean difference = 11.0) which corresponds to expected means of $\mu = 96$ for the 50,000 IU group and $\mu = 85$ for the 5,000 IU dose group, and that the common within-group standard deviation is one standard deviation (or 15 points). This effect was selected as the smallest effect that would be important to detect, in the sense that any smaller effect would not be of clinical or substantive significance. In order to account for attrition, 80 participants are planned to enroll into the study.

Statistical Analysis Plan

Summary frequencies will be reported by treatment allocation for all nominal baseline characteristics, including sex, race, ethnicity, marital status, season of first dose, and physical activity level. Summary statistics will be similarly reported as mean with standard deviation for normally distributed demographics (i.e., age, body mass index, blood pressures and heart rate, and CES-D score), while median with interquartile range will be reported for other summary measures including PHQ-9 score, WRAT-IV reading sub-score, years of education, and laboratory values (i.e., vitamin D level, HbA1c, glucose, creatinine, and calcium).

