Regarding performance on the *executive functioning* assessments, linear mixed-effects models will be used to estimate the mean change in participants' standardized scores as a function of elapsed time since baseline, treatment assignment, and their interaction. In this study, patients will contribute multiple scores to the analysis and random intercepts will be allowed for each patient to account for their within-subject correlation using an unstructured covariance structure. Regarding model fit, linearity and normality will be assessed using residual and QQ plots, respectively, while outliers will be assessed using box plots. A similar approach will be used to assess performance on assessments of *language and memory* functioning.

Regarding change in *quality of life* and *functioning* self-report measures (i.e., the SAS-SR; SCI-R; PAID; EWPS; PSQI; MOS; and PSS), each participant's baseline score will be subtracted from his/her week 13 score. Subsequently, an independent samples t -

test will be used to compare this change score between participants assigned to the high dose versus those assigned to the low dose. In these comparisons, the distribution of survey scores will be assessed for normality using QQ plots and for outliers using box plots. When survey scores are not normally distributed, an exact version of the Wilcoxon rank-sum test may be used to confirm parametric conclusions.

Finally, summary frequencies will be reported for all reported adverse events during the trial by treatment allocation. This includes the number of affected individuals at risk for the adverse event as well as the number of times the adverse event was reported. All analyses will be completed using SAS version 9.4 (Cary, NC).

Literature Cited

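### Self-report scales, including both self-management measures, are compared by change-score t-test; adjusting for the baseline score already collected would usually be more precise

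*Combined protocol and SAP*

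**What the plan says.** The Statistical Analysis Plan section lists seven self-report scales ("SAS-SR; SCI-R; PAID; EWPS; PSQI; MOS; and PSS"). For each, the participant's "baseline score will be subtracted from his/her week 13 score", and an independent-samples *t* "test will be used to compare this change score between participants assigned to the high dose versus those assigned to the low dose". Normality and outliers are checked on the scores. If scores are not normal, "an exact version of the Wilcoxon rank-sum test may be used to confirm parametric conclusions". No covariate appears in either analysis. The mixed models in the same section cover executive function, language and memory, not these scales.

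The secondary aim in Study Aims is "To determine the effect of vitamin D₃ supplementation on diabetes self-management", with a hypothesis that compares the arms at three months. Part B of Measurements, which opens "Self-Management measures include", names the Diabetes Self-Care Inventory and the diabetes-distress scale. I read these as SCI-R and PAID in the analysis text. Study Procedures and Table 1 schedule the questionnaires at baseline and week 13.

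The power section concerns executive function only: with 62 participants, "the study has power of 81.1% to yield a statistically significant result". It says nothing about the self-report scales.

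**The concern.** A change score subtracts the whole baseline value, which amounts to assuming that the week 13 score rises one unit for each unit of baseline. Questionnaire scores often regress toward the mean, and the slope is then below 1. Subtracting the full baseline over-corrects for chance imbalance between arms and adds baseline noise to the comparison. Regression on arm and baseline score (ANCOVA) estimates the slope from the data.

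Validity is not at stake, because both estimators are unbiased under randomization. What is at stake is the width of the interval for self-management, a stated aim with no power calculation of its own, in a trial that counts on 31 per arm.

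**Working it through.** **Inputs from the documents.** 62 participants, 1:1, so n = 31 per arm; two-sided alpha 0.05; for the primary outcome, difference 11 and SD 15 (Statistical Methods: Power).

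**Assumptions.** The documents give no SD, correlation or target difference for the seven scales. I take the week 13 SD as 1, the baseline SD as k, the baseline-to-week-13 correlation as r, and an illustrative true difference of 0.5 SD.

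**The plan's own figure.** Noncentrality = 11 / (15 × √(2/31)) = 2.89 with 60 df. The noncentral t gives 81.1%, as stated; the normal approximation gives 82.3%. The method therefore matches the plan's.

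**Variances per participant.**
- Change score: 1 + k² − 2rk, which is 2(1 − r) when k = 1.
- ANCOVA: (1 − r²) × 59/58. The factor is the expected price of estimating the slope at N = 62: 1 + 1/(62 − 4) = 59/58 = 1.017. Residual df fall from 60 to 59.
- Ratio when k = 1: (1 + r)/2 × 59/58. It reaches 1 at r = 2 × 58/59 − 1 = 0.966.

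**Worked case, r = 0.5, k = 1.** The change-score variance is 1.00, so SE = √(1.00 × 2/31) = 0.254. The ANCOVA variance is 0.75 × 59/58 = 0.763, so SE = √(0.763 × 2/31) = 0.222, which is 13% smaller. Power for 0.5 SD is 49.1% against 60.1%.

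**Over the range, k = 1.**

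| r | Variance ratio | SE reduction | Power at 0.5 SD, change vs ANCOVA | Difference detectable at 80% power (SD), change vs ANCOVA |
|---|---|---|---|---|
| 0.3 | 0.661 | 19% | 37.4% vs 52.1% | 0.86 vs 0.70 |
| 0.5 | 0.763 | 13% | 49.1% vs 60.1% | 0.72 vs 0.63 |
| 0.6 | 0.814 | 10% | 58.1% vs 67.0% | 0.65 vs 0.58 |
| 0.7 | 0.865 | 7% | 70.6% vs 76.7% | 0.56 vs 0.52 |
| 0.8 | 0.916 | 4% | 86.5% vs 89.2% | 0.46 vs 0.44 |
| 0.9 | 0.966 | 2% | 99.1% vs 99.3% | 0.32 vs 0.32 |

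In variance terms, a change-score analysis would need about 31/0.763 = 41 per arm at r = 0.5, or 31/0.865 = 36 at r = 0.7, to match ANCOVA with 31. When r < k/2 (below 0.5 at equal SDs), the change score is less precise than ignoring baseline altogether.

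**Unequal SDs.**

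| Baseline SD / week 13 SD | Ratio at r = 0.5 | r = 0.7 | r = 0.8 |
|---|---|---|---|
| 0.8 | 0.91 | 1.00 | 1.02 |
| 1.2 | 0.62 | 0.68 | 0.70 |

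The 1.02 is the worst case for ANCOVA: the slope r/k = 0.8/0.8 is exactly 1, and only the 59/58 penalty is left.

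**Simulation check** (20,000 trials per setting, k = 1). At r = 0.3, 0.5, 0.7 and 0.9, type I error was 5.0–5.3% for the change score and 5.0–5.4% for ANCOVA. Both estimators averaged 0.499–0.501 for a true 0.5. Power was 48.9% vs 60.2% at r = 0.5 and 70.3% vs 76.6% at r = 0.7.

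**The case against.** The strongest case against is that nothing here is wrong. Both analyses are valid, the scales are secondary, the trial is small and calls itself a pilot, and the primary power does not move. The gain also rests on assumed values. At r = 0.9 it is negligible, and with a baseline SD 0.8 of the week 13 SD it is nil at r = 0.7. Excluding people with CES-D of 16 or more may narrow the baseline spread of mood-related scales. In an assumed example with slope 0.7 and residual variance 0.51, halving the baseline variance from 1 to 0.5 moves the ratio from 0.86 to 0.93. Only two of the seven scales serve a stated hypothesis, and MOS is not described in Measurements at all.

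All of that stands as a limit on size and weight. It does not remove the point: the possible expected loss is capped at 1.7% of variance, the possible gain is much larger, and the price is close to nothing.

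Two drafting objections also stand. More than one sentence has to change. And if the Wilcoxon test goes on ranking unadjusted change, it keeps the slope at 1 and does not check the new model.

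**Conclusion.** The point holds as an improvement in efficiency, not as an error. The planned test uses the baseline score in a way that is generally less precise than adjustment. With 31 per arm and equal SDs, the variance falls by about 34% at r = 0.3, 24% at 0.5, 14% at 0.7 and 3% at 0.9. The actual gain cannot be fixed from the documents, because they give neither correlations nor SDs. It shrinks as the true slope nears 1, where ANCOVA costs 1.7% in variance. It matters most for SCI-R and PAID, which carry the secondary aim. The executive-function analysis and the 81.1% are untouched.

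**What to change.** In the Statistical Analysis Plan section, replace the subtraction and t-test for the seven scales with a linear regression of the week 13 score on treatment arm and baseline score. Report the adjusted difference between arms with its 95% confidence interval as the planned result, and apply the QQ and box plots to the model residuals. The exact Wilcoxon test can stay as a sensitivity analysis, but the text should say what it ranks. One option is the residuals from regressing the week 13 score on baseline with arms pooled.

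Make the change before treatment codes are opened, so that the method is not chosen after seeing results. The cost is a few sentences in one paragraph, one SAS model statement per scale and one residual degree of freedom (60 to 59). No new data are needed and no participants are lost, because the change score already needs both scores.
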